5.1 Inclusion Criteria

Participants are eligible to be included in the study only if all of the following criteria apply:

Age

1. Participant must be at least 18 years of age at the time of signing the ICF.

Type of Participant and Disease Characteristics

2. Participants with ESRD on HD for ≥3 months at the time of signing of the ICF, receiving dialysis at least 9 hours a week and stable in the view of the investigator.¹

¹ See section 5.4 for information on rescreening.

07 JUL 2021 Page: 33 of 90

Sex

3. Male or female Contraceptive use by men or women should be consistent with local regulations regarding the methods of contraception for those participating in clinical studies.².

Informed Consent

4. Capable of giving signed ICF as described in Section 10.1.3 which includes compliance with the requirements and restrictions listed in the ICF and in this protocol

5.2 Exclusion Criteria

Participants are excluded from the study if any of the following criteria apply:

Prior/Concomitant Therapy

- 1. Receiving antiplatelet therapy except daily ASA \leq 150 mg/day
- 2. Receiving anticoagulation in therapeutic doses, other than standard anticoagulation during the hemodialysis procedure.

Medical Conditions

- 3. Known inherited bleeding disorder e.g. von-Willebrand disease or Hemophilia A, B or C
- 4. Recent (<6 months before screening) clinically significant bleeding, or at high risk of bleeding (in the judgement of the investigator)
- 5. Recent (<3 months before screening) thromboembolic event, e.g. acute coronary syndrome, stroke, or VTE (except dialysis access thrombosis)
- 6. Recent (<3 months before screening) major surgery or scheduled major surgery during participation in the study
- 7. Scheduled living donor renal transplant during study participation
- 8. Known Hepatitis B or C
- 9. Known HIV with recent documented detectable viral load (<3 months before screening)
- 10. Persistent heart failure as classified by the New York Heart Association classification of 3 or higher
- 11. Life expectancy less than 6 months
- 12. Sustained uncontrolled hypertension (persistent measurements of diastolic blood pressure ≥ 100 mmHg, and/or systolic blood pressure ≥180 mmHg)
- 13. Hepatic disease associated with either: coagulopathy leading to a clinically relevant bleeding risk, or ALT > 3x ULN, or total bilirubin >2x ULN with direct bilirubin > 20% of the total

² See Section 10.4 for requirements on contraception

07 JUL 2021 Page: 34 of 90

- 14. Hb < 9.0 g/dL at screening³
- 15. Platelet count < 120,000 / mm³ at screening³
- 16. Known hypersensitivity to the investigational drug or to inactive constituents of the study intervention
- 17. Active malignancy requiring treatment during study participation (except non-melanoma skin cancer, or cervical carcinoma in situ)

Prior/Concurrent Clinical Study Experience

18. Participation in a study with an investigational medicinal product within 30 days or within 5 half-lives of the previous administered drug, whichever is longer, prior to the screening period

Note: Participants from previous BAY 2306001/ISIS 416858 and BAY 2976217 / ION 957943 studies are eligible.

Other Exclusions

- 19. Any other conditions, which, in the opinion of the investigator or Sponsor would make the subject unsuitable for inclusion
- 20. Confirmed pregnancy

5.3 Lifestyle Considerations

No lifestyle restrictions are required.

5.4 Screen Failures

Screen failures are defined as participants who consent to participate in the clinical study but are not subsequently randomly assigned to study intervention. A minimal set of screen failure information is required to ensure transparent reporting of screen failure participants to meet the Consolidated Standards of Reporting Trials (CONSORT) publishing requirements and to respond to queries from regulatory authorities. Minimal information includes demography, screen failure details, and eligibility criteria.

Individuals who do not meet the criteria for participation in this study (declared as screen failure) may be rescreened once.

The investigator should ensure that the resolution of a prior exclusionary circumstance or condition is fully resolved.

The investigator has to ensure that the repeated screening procedures do not expose the participant to an unjustifiable health risk. In addition, the participant must re-sign the ICF during re-screening. Rescreened participants will be assigned a new participant number and all assessments for the study must be repeated.

³ One re-assessment of hemoglobin and platelet levels is allowed during the screening period.

07 JUL 2021 Page: 35 of 90

6. Study Intervention

Study intervention is defined as any investigational intervention(s), marketed product(s), placebo, or medical device(s) intended to be administered to a study participant according to the study protocol.

6.1 Study Intervention(s) Administered

Table 6-1: Study interventions administered

Arm Name	BAY 2976217	Placebo
Intervention Name	BAY 2976217	Placebo
Type	Drug	Placebo
Dose Formulation	solution for injection	solution for injection
Unit Dose Strength(s)	100 mg/mL	not applicable
Dosage Level(s)	40 mg, 80 mg or 120 mg (or	• •
3 ()	100 mg if dose reduction is	not applicable
	recommended by DMC)	• •
Route of	SC injection	SC injection
Administration	,	,
Use	Experimental	Placebo
Packaging and	Study intervention will be provided	Study intervention will be provided
Labeling	in 2 mL colorless vials.	in 2 mL colorless vials. Each vial
	Each vial will be labelled as	will be labelled as required per
	required per country requirement.	country requirement.
Current/Former	ION-957943	not applicable
Name(s) or Alias(es)	10.11 00.70 10	пос арриоавіо

DMC = Data Monitoring Committee, SC = Subcutaneous

BAY 2976217 is supplied in 2 mL clear, single-use injection glass vials as a solution. BAY 2976217 is a solution with a concentration of 100 mg/mL. The total content of the glass vial is approximately 1.05 mL, corresponding to 100 mg BAY 2976217. From the total 1.05 mL, 0.8 mL (i.e. 80 mg) are extractable volume and 0.25 mL (i.e. 25 mg) are overfill.

Placebo to BAY 2976217 is supplied in 2 mL clear, single-use glass vials as a solution with a content of 1.05 mL (0.8 ml extractable volume). Further details can be found in the handling instruction provided separately.

Different doses will be achieved by administering a different volume. For dosage regimen and planned duration of intervention see Section 4.1.

Study intervention will be administered any time from 15 minutes before the start of dialysis to 15 mins after the start of dialysis, when administered on a dialysis day.

Study intervention can be administered in the following SC injection areas:

- Abdomen (upper right, upper left, lower right, lower left)
- Thigh
- Outer area of upper arm

Note: Injection is not to be given within two inches (5cm) of any of the following: the umbilicus, the active reaction area of a previous injection, or in areas of the skin that are burned, reddened, inflamed, or swollen. Injections may be administered to a location that previously was involved in an injection site response provided that any symptoms have largely resolved.

07 JUL 2021 Page: 36 of 90

6.2 Preparation/Handling/Storage/Accountability

- 1. The investigator or designee must confirm appropriate temperature conditions have been maintained during transit for all study intervention received and any discrepancies are reported and resolved before use of the study intervention.
- 2. Only participants enrolled in the study may receive study intervention and only authorized site staff may supply or administer study intervention. All study intervention must be stored in a secure, environmentally controlled, and monitored (manual or automated) area in accordance with the labeled storage conditions with access limited to the investigator and authorized site staff.
- 3. The investigator, or the head of the institution (where applicable) is responsible for study intervention accountability, reconciliation, and record maintenance (i.e., receipt, reconciliation, and final disposition records).
- 4. Further guidance and information for the final disposition of unused study interventions are provided in the investigator site file.

6.3 Measures to Minimize Bias: Randomization and Blinding

After a participant has signed an ICF, the unique PID will be assigned via IWRS. If a participant is re-screened, a new PID will be assigned. The PID is a 9-digit number consisting of:

Digits 1 to 5 =Unique site number

Digits 6 to 9 = Unique participant number (current participant number within the study site). The unique participant number will start with 7 for each participant.

All participants will be centrally assigned to randomized study intervention using IWRS. Study intervention will be administered at the study visits summarized in SoA (Section 1.3). Before the study is initiated, the log in information and directions for the IWRS will be provided to each site

Participants who meet the entry criteria will be randomized as described in Section 4.1 Participants will be stratified as described in Section 4.1

In order to be able to prepare and administer the correct volume of study intervention to be injected, sponsor, participants and investigators will be aware of dose cohort assignment, but blinded with respect to active treatment versus matching placebo. The CIAC will be blinded to cohort allocation and treatment assignment. DMC will have access to unblinded data as outlined in the DMC charter.

In order to maintain the blind, BAY 2976217 and matching placebo will be packaged in identical vials and each vial will be labeled with a unique, pre-printed number.

The IWRS will be programmed with blind-breaking instructions. In case of an emergency, the investigator has the responsibility for determining if unblinding of a participant's intervention assignment is warranted. If the investigator is unavailable, and a treating physician not associated with the study requests emergency unblinding, the emergency unblinding requests are forwarded to the emergency medical advice 24 hours/7-day service. Participant safety must always be the first consideration in making such a determination. If the investigator decides that unblinding is warranted, the investigator should make every effort to contact the sponsor prior to unblinding a participant's intervention assignment unless this could delay emergency treatment of the participant. If a participant's intervention assignment is

07 JUL 2021 Page: 37 of 90

unblinded, the sponsor must be notified within 24 hours after breaking the blind. The date and reason that the blind was broken must be recorded in the source documentation and case report form, as applicable.

Central lab results for PD parameters including coagulation parameters will not be provided to the sites or other blinded personnel, as these are potentially unblinding. Investigators will also avoid local testing of coagulation parameters, as these may be unblinding, unless clinically indicated.

Bioanalytics and pharmacometrics staff will be unblinded according to Bayer SOPs. Bioanalysis and popPK evaluation might be started prior to database lock: if this is applicable, appropriate measures will be taken to maintain blinding of the study team, e.g., data will be stored separately, and members of the study team will not have access to the unblinded data.

6.4 Study Intervention Compliance

Participants are dosed at the site, and they will receive study intervention directly from the investigator or other qualified and trained staff. The date and time of each dose administered in the clinic will be recorded in the source documents and recorded in the eCRF. The vial number(s) and study participant identification will be confirmed at the time of dosing. To monitor compliance, drug accountability information will be documented for each participant.

6.5 Concomitant Therapy

Prior medications that should be stopped at least 5 days prior to the first study intervention (if clinically appropriate) and are not allowed concomitantly with the study intervention are:

- Antiplatelets except ASA ≤ 150 mg/day (e.g., clopidogrel, ticagrelor, prasugrel, dipyridamole, ASA >150 mg/day).
 - o If a participant is taking low dose ASA (≤150mg/day) at randomization, the dosage should not be changed during the study, unless clinically indicated; if the dose is permanently increased >150 mg/day the participant should discontinue study intervention.
 - All efforts should be made during the treatment period to avoid change in ASA use, unless clinically indicated
- Anticoagulant agents (e.g., VKAs such as phenprocoumon, warfarin-sodium, or DOAC oral anticoagulants such as rivaroxaban, apixaban, dabigatran, UFH, LMWH, etc.).
- UFH or LMWH other than used during the hemodialysis session to prevent clotting of dialysis circuit or to maintain patency of hemodialysis access.

If a prohibited concomitant medication is indicated, study intervention will be temporarily interrupted.

In case study intervention is interrupted for >56 days, the participant will be discontinued from study intervention as described in Section 7.2.

In case study intervention is interrupted for \leq 56 days, study intervention may be restarted as per SoA after the concomitant medication is no longer used.

07 JUL 2021 Page: 38 of 90

Any medication or vaccine (including over-the-counter or prescription medicines, vitamins, and/or herbal supplements) that the participant is receiving at the time of signing of the ICF or receives during the study must be recorded along with:

- Reason for use
- Dates of administration including start and end dates
- Dosage information including dose and frequency

Specifically, anticoagulants and antiplatelet agents taken within 30 days prior to Visit 1 even if taken before the ICF was signed should also be recorded in the eCRF.

The Medical Monitor should be contacted if there are any questions regarding concomitant or prior therapy.

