7.1.1 Events Requiring Definitive Discontinuation of Study Intervention

A participant must permanently discontinue study intervention for any of the following:

- The participant becomes pregnant. The pregnancy will be reported per reporting procedures in Section 8.3.5.
- The participant is unwilling to continue study intervention.
- The participant experiences an AE (including clinically significant bleeding [Sections 8.2.1 and 8.3]) that in the judgment of the investigator necessitates permanent discontinuation of study intervention.
- Requires surgery that in the judgment of the investigator necessitates permanent discontinuation of study intervention.
- The participant develops laboratory test abnormalities that meet any of the stopping rules listed in Section 8.3.8.1.2 and 8.3.8.2.2.
- The participant is no longer on maintenance hemodialysis (including hemodiafiltration) for a minimum of 9 hours per week, including a change in dialysis modality (e.g. peritoneal dialysis) or renal transplantation.
- The participant moves their dialysis care to a different hemodialysis facility where the study team cannot continue to follow the participant.
- The participant begins treatment with a disallowed concomitant medication and the study intervention is interrupted for >56 days, as described in Section 6.5.

When a study participant discontinues the study intervention early:

- During the main treatment period, the participant should conduct Visit 22 four weeks after the last dose of study intervention
- During the extended treatment period, the participant will conduct Visit 28 four weeks after the last dose of study intervention
- In both cases, the participant will then enter the 16-week follow-up period, giving a total of 20 weeks of follow-up from the last dose of study intervention.

If the participant moves their dialysis care to a different hemodialysis facility where the study team cannot follow the participant, all efforts should be made to conduct the evaluation and post-treatment follow-up visits in person to complete all study procedures. If in-person visits by the participant are impossible, limited remote contact visits (e.g. phone) may be conducted recording as much information as possible for eCRF entry. The reason for discontinuation of study intervention must be recorded in the eCRF and source documentation.

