7.2 Participant Discontinuation/Withdrawal from the Study

- A participant may withdraw from the study at any time at his/her own request, or may be withdrawn at any time at the discretion of the investigator for safety, behavioral, compliance, or administrative reasons. This is expected to be uncommon. If the participant withdraws consent, or the investigator withdraws the participant, the reason for withdrawal should be recorded on the eCRF.
- Additional reasons for withdrawal from the study:
 - Death of participant, in which case only relevant eCRF pages will be completed (e.g.- AEs [including the cause of death] and concomitant medications up to death, vital status, etc).
 - The participant signs-off dialysis without expected return of life-sustaining kidney function or without transferring to an alternative form of renal-replacement therapy, the reason for withdrawal of renal replacement therapy should be recorded on the eCRF.
 - o If a stopping rule is met (see Sections 8.3.8.1.2, 8.2.1.1 and 8.3.8.2.2) during the screening period, the participant should be screen-failed.
- At the time of discontinuing from the study, if possible, an early termination visit should be conducted, as shown in the SoA. See SoA for data to be collected at the time of study discontinuation and follow-up and for any further evaluations that need to be completed.
- The participant will be permanently discontinued both from the study intervention and from the study at that time.
- If the participant withdraws consent for disclosure of future information, the sponsor may retain and continue to use any data collected before such a withdrawal of consent.

If a participant is permanently discontinued/withdrawn from the study, the Early Termination Visit in the SoA will be conducted immediately. All study outcomes will be censored at Early Termination.

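### Protocol 6.5 refers interruptions of more than 56 days for a prohibited drug to the study-withdrawal section, while 7.1.1 gives the same case 20 weeks of follow-up after the last dose

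*Protocol*

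**What the plan says.** Protocol 6.5 (Concomitant Therapy) requires study drug to be interrupted when a prohibited medication is indicated, and then states that, once the interruption exceeds 56 days, "the participant will be discontinued from study intervention as described in Section 7.2".

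The section it refers to is headed "7.2 Participant Discontinuation/Withdrawal from the Study". Its consequences are: "The participant will be permanently discontinued both from the study intervention and from the study at that time". An Early Termination Visit follows immediately, and "All study outcomes will be censored at Early Termination".

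Protocol 7.1.1 lists the same event among the reasons for definitive discontinuation of study intervention: "The participant begins treatment with a disallowed concomitant medication and the study intervention is interrupted for >56 days, as described in Section 6.5". There, a participant who stops during the main treatment period is told that "the participant should conduct Visit 22 four weeks after the last dose of study intervention" (Visit 28 if in the extension). The 16-week follow-up period comes next, "giving a total of 20 weeks of follow-up from the last dose of study intervention".

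Three other places describe stopping drug without leaving the study:
- Protocol 7.1 keeps participants in the study for outcome evaluation after definitive discontinuation of drug.
- Protocol 7.1.2 names temporary use of prohibited medication and, beyond 56 days from the last dose, calls the result permanent discontinuation from study intervention.
- SAP 4.2.1 sends participants interrupted beyond 56 days into the post-treatment follow-up period.

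**The concern.** One event has two procedures attached to it. Under 7.1.1 the participant stops drug and is followed for 20 weeks from the last dose. Under the section that 6.5 cites, the participant leaves the study and outcome collection ends. Section 7.2 contains no procedure for stopping drug while remaining in the study, so the 6.5 reference cannot be read as pointing to a milder rule within it. Starting from 7.1.1 does not settle the matter either, because its bullet cites 6.5, and 6.5 cites 7.2.

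At stake is the post-dose safety follow-up. Protocol 2.3 justifies about five months of observation after the last dose by the drug's prolonged pharmacodynamic effect. A participant removed by this route would be missing for part of that period, shortly after using a drug that the protocol disallows alongside study treatment. The SAP (Table 5-2) labels the OA analyses of the clinical endpoints as treatment policy, and censoring at an event tied to treatment interruption does not fit that label.

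**Working it through.** **The passages side by side**

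| Place | Status after more than 56 days | Follow-up |
|---|---|---|
| Protocol 6.5 | Off study intervention, procedure by reference to 7.2 | As 7.2 |
| Protocol 7.2 | Off intervention and off study | Immediate Early Termination Visit, outcomes censored |
| Protocol 7.1.1 | Off study intervention | Visit 22 or 28, then 16 weeks |
| Protocol 7.1 | Off study intervention, stays in study | As 7.1.1 |
| Protocol 7.1.2 | Off study intervention | Not stated |
| SAP 4.2.1 | Off study intervention | Post-treatment follow-up period |

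**The plan's own figure.** Visit 22 or 28 is 4 weeks after the last dose, and 16 weeks follow: 4 + 16 = 20 weeks = 20 × 7 = 140 days. This reproduces the 20 weeks in 7.1.1.

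**Follow-up lost if 7.2 is applied literally.** Section 6.5 does not say when its 56 days begin, so two cases are shown. The earliest exit is the first day beyond 56.

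- *Clock from the last dose* (stated in 7.1.2 and SAP 4.2.1): exit on day 57. Loss = 140 − 57 = 83 days; 83/140 = 59%, or about 12 weeks.
- *Clock from the first missed dose* (assumption; dosing is every 4 weeks, so that dose is due on day 28): exit on day 28 + 57 = 85. Loss = 140 − 85 = 55 days; 55/140 = 39%, or about 8 weeks.

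Each is the most that can be lost under its clock. A later exit loses less.

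**Which analyses are reached**

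- *On-treatment window* (Protocol 9.4.1.6): closes 28 days after the last dose. Both 57 and 85 exceed 28. Under SAP 4.5.1 and 4.5.2 the PA and TA scopes end no later than last dose + 28 days for someone who stops early. The primary bleeding endpoint and the TA analyses are therefore complete before the exit.
- *TEAEs to 20 weeks after the last dose* (Protocol Table 3–1 and 9.4.3, a secondary endpoint): truncated.
- *OA scope* (SAP 4.5.2, to the end of follow-up; labelled exploratory for the primary, secondary and exploratory endpoints in Table 5-2): truncated.
- *Follow-up samples* (Protocol Table 8–1): PK/PD is due at FU1 and FU4, and immunogenicity at FU4. FU visits are 4 weeks apart, so FU1 falls at 4 + 4 = 8 weeks (day 56) and FU4 at day 140. FU4 is lost under either clock. FU1 falls close to a day-57 exit and may be replaced by the Early Termination sample.

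Table 5-2 also assigns the OA scope to the main PK and PD endpoints. Those are pre-dose troughs and maximum FXI changes within the main treatment period, so the exit does not remove them.

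**The case against.** The strongest reply is that this is one misdirected section number. The words of 6.5 stop study intervention; they do not say that the participant leaves the study. Section 7.2 does not name prohibited medication among its withdrawal reasons, and its Early Termination Visit and censoring apply to someone withdrawn from the study. Sections 7.1, 7.1.1 and 7.1.2 and SAP 4.2.1 are consistent with one another, and 6.5 tells sites to contact the Medical Monitor with questions on concomitant therapy. Most sites may well have kept these participants in follow-up.

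Much of this stands. A reader might infer that the protocol plainly orders these participants out of the study. The documents do not support that: the conflict arises only through the cross-reference.

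A reader might also infer that those lost would be a selected group at high bleeding risk, often treated after a thrombotic event, so that safety comparisons would be biased. The documents give neither the reasons for starting such drugs in this trial, nor the bleeding risk of those who do, nor any count by arm. Differential loss is possible but not shown.

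What does not fall away is that 6.5 is operative text giving sites an instruction, that 7.1.1 leads back to it, and that the section it cites contains only a withdrawal procedure. Agreement elsewhere makes the conflict easier to resolve but leaves the instruction in place.

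**Conclusion.** The inconsistency is real and should be corrected. Its effect is limited to post-treatment safety and sampling data. Read literally, the reference costs an affected participant up to 83 of 140 days of follow-up (59%) with the clock from the last dose, or up to 55 of 140 (39%) with the clock assumed to start at the first missed dose. A flat figure of 12 weeks holds only for the first case.

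A reader might infer that the primary result is at risk. It is not, because the 28-day on-treatment window has closed before either exit day.

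The size rests on two assumptions: that a site followed the reference literally, and that it did so as soon as 56 days had passed. The number of participants affected is not given and may be zero. No view is taken here on which clinical rule should apply.

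**What to change.** Reconcile Protocol 6.5, 7.1.1 and 7.2 and SAP 4.2.1 so that one procedure and one follow-up schedule apply to interruption beyond 56 days for a prohibited medication, and state in 6.5 when the 56 days begin. The reconciled text should also say which visits apply: the Visit 22 or 28 time point in 7.1.1, 4 weeks after the last dose, has already passed when the 56-day limit is reached.

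Notify sites of the reconciled text. Before the final analysis, list any participant withdrawn and censored by this route, with arm, last dose date and exit date, and state in the SAP how they are handled, so that the 20-week TEAE and OA analyses treat them consistently.

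The cost is a corrected reference with a clarifying sentence or two, a note to sites and one data check. No design, sample size or primary analysis changes.
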